#### Comments:

The objective of this study is to measure awareness of surgeons. There is no exposure measured.

	ion 6: Outcome definition and surement	Yes	No	N/ A	Section Number
6.1	Does the protocol specify the primary and secondary (if applicable) outcome(s) to be investigated?			$\boxtimes$	
6.2	Does the protocol describe how the outcomes are defined and measured?			$\boxtimes$	
6.3	Does the protocol address the validity of outcome measurement? (e.g. precision, accuracy, sensitivity, specificity, positive predictive value, use of validation sub-study)				
6.4	Does the protocol describe specific outcomes relevant for Health Technology Assessment? (e.g. HRQoL, QALYS, DALYS, health care services utilisation, burden of disease or treatment, compliance, disease management)				
Comn	nents:				
This	study doesn't measure outcomes but awareness	s of su	rgeons		
Sect	tion 7: Bias	Yes	No	N/ A	Section Number
7.1	Does the protocol address ways to measure confounding? (e.g. confounding by indication)			$\boxtimes$	
7.2	Does the protocol address selection bias? (e.g. healthy user/adherer bias)	$\boxtimes$			
7.3	Does the protocol address information bias? (e.g. misclassification of exposure and outcomes, time-related bias)				
Comn	nents:				
	n the nature of the study, confounders are not $\epsilon$ measured.	expecte	ed. The	erefore	, these are
C 1	in O Effect measure modification	Yes	No	N/A	Section
Seci	ion 8: Effect measure modification	103	110	14/11	Number
8.1	Does the protocol address effect modifiers? (e.g. collection of data on known effect modifiers, subgroup analyses, anticipated direction of effect)				
Comments:					
Given the nature of the study effect modifiers are not expected. Therefore, these are not measured.					
Sect	tion 9: Data sources	Yes	No	N/ A	Section Number
9.1	Does the protocol describe the data source(s) used in the study for the ascertainment of:				

Section 9: Data sources		Yes	No	N/ A	Section Number
	9.1.1 Exposure? (e.g. pharmacy dispensing, general practice prescribing, claims data, self-report, face-to-face interview)			$\boxtimes$	
	9.1.2 Outcomes? (e.g. clinical records, laboratory markers or values, claims data, self-report, patient interview including scales and questionnaires, vital statistics)				
	9.1.3 Covariates and other characteristics?				9.3
9.2	Does the protocol describe the information available from the data source(s) on:				
	9.2.1 Exposure? (e.g. date of dispensing, drug quantity, dose, number of days of supply prescription, daily dosage, prescriber)				
	9.2.2 Outcomes? (e.g. date of occurrence, multiple event, severity measures related to event)			$\boxtimes$	
	9.2.3 Covariates and other characteristics? (e.g. age, sex, clinical and drug use history, comorbidity, co-medications, lifestyle)	$\boxtimes$			9.3
9.3	Is a coding system described for:				
	9.3.1 Exposure? (e.g. WHO Drug Dictionary, Anatomical Therapeutic Chemical (ATC) Classification System)				
	9.3.2 Outcomes? (e.g. International Classification of Diseases (ICD), Medical Dictionary for Regulatory Activities (MedDRA))			$\boxtimes$	
	9.3.3 Covariates and other characteristics?		$\boxtimes$		
9.4	Is a linkage method between data sources described? (e.g. based on a unique identifier or other)		$\boxtimes$		
Comments:					
There is no coding planned for covariates and other characteristics, nor is there a linkage foreseen between different data sources.			is there a		
Sect	ion 10· Analysis nlan	Ves	Nο	NI/	Section

Section 10: Analysis plan		No	N/ A	Section Number
10.1 Are the statistical methods and the reason for their choice described?				9.7
10.2 Is study size and/or statistical precision estimated?				9.5
10.3 Are descriptive analyses included?	$\boxtimes$			9.7
10.4 Are stratified analyses included?		$\boxtimes$		
10.5 Does the plan describe methods for analytic control of confounding?			$\boxtimes$	
10.6 Does the plan describe methods for analytic control of outcome misclassification?			$\boxtimes$	

				pago 20 01 00	
Section 10: Analysis plan	Yes	No	N/ A	Section Number	
10.7 Does the plan describe methods for handling missing data?			$\boxtimes$		
10.8 Are relevant sensitivity analyses described?	$\square$			9.7	
Comments:					
There are no confounders (see above) or outcomes measured in this study.					
As the study population will only include completed description needed for the handling of missing data	-	nnaire	es ther	e is no	
Section 11: Data management and quality control	Yes	No	N/ A	Section Number	
11.1 Does the protocol provide information on				Hamber	
data storage? (e.g. software and IT environment, database maintenance and anti-fraud protection, archiving)				9.6	
11.2 Are methods of quality assurance described?	$\boxtimes$			9.8	
11.3 Is there a system in place for independent review of study results?		$\boxtimes$			
Comments:	l .	I			
There is no independent review of the study results however, the study results will be shared with the leader to be shared with the	•	•		•	
12.1 Does the protocol discuss the impact on the study results of:					
12.1.1 Selection bias?	$\boxtimes$			9.9	
12.1.2 Information bias?				9.9	
12.1.3 Residual/unmeasured confounding?					
(e.g. anticipated direction and magnitude of such biases, validation sub-study, use of validation and external data, analytical methods).					
12.2 Does the protocol discuss study feasibility?  (e.g. study size, anticipated exposure uptake, duration of follow-up in a cohort study, patient recruitment, precision of the estimates)				9.1	
Comments:					
As described above, there is no confounding expec-	ted for t	his stu	ıdy.		
Section 13: Ethical/data protection issues	Yes	No	N/	Section	
12.1 Have requirements of Ethics Committee /			Α	Number	
13.1 Have requirements of Ethics Committee/ Institutional Review Board been described?			$\boxtimes$		

Section 13: Ethical/data protection issues	Yes	No	N/ A	Section Number
13.2 Has any outcome of an ethical review procedure been addressed?			$\boxtimes$	
13.3 Have data protection requirements been described?	$\boxtimes$			10
Comments:				
For this study no ethical committee review is require	ed.			
	1	ı	1	
Section 14: Amendments and deviations	Yes	No	N/ A	Section Number
14.1 Does the protocol include a section to document amendments and deviations?				5
Comments:				
Г а	T			
Section 15: Plans for communication of study results	Yes	No	N/ A	Section Number
15.1 Are plans described for communicating study results (e.g. to regulatory authorities)?				12
15.2 Are plans described for disseminating study results externally, including publication?				12
Comments:				
Name of the main author of the protocol: [name]				
Date: Captured with electronic signature				
Signature : Signed electronically				

# **Annex 3. Questionnaire**

# Demographic questions

Please indicate your specialty (select one response):

- (1) Neurosurgery
- (2) Traumatology
- (3) Orthopaedic surgery
- (4) Other

Please indicate your practice type (select one response):

- (1) General / non-university public hospital (not affiliated with university hospital)
- (2) Academic teaching hospital
- (3) Private Hospital or Clinic
- (4) Other (please specify): [MULTILINE INPUT]

In total, how many years have you been a practicing physician?

- $(1) \le 5$  years
- (2) 6-10 years
- $(3) \ge 10$  years
- (4) Prefer not to answer

## Questionnaire on InductOs

How many years have you been using InductOs?

- $(1) \le 5$  years
- (2) 6-10 years
- $(3) \ge 10$  years
- (4) Prefer not to answer

When was the last time you implanted InductOs?

- (1) 0 <3 months ago
- (2) 3 <6 months ago
- (3) 6 <9 months ago
- (4) 9 < 12 months ago
- (5) 12 24 months ago
- (6) I don't remember

Approximately how many patients have you implanted with InductOs in the past 2 years?

- (1) < 5
- (2) 5 < 10
- (3) 10-<15
- (4) 15-<20
- (5) > 20
- (6) I don't know

Please indicate in percentages how much of your time is spent in the following approaches during your procedures with InductOs. Must sum to 100%.

- (1) Anterior Lumbar Interbody Fusion (ALIF)
- (2) Posterior Lumbar Interbody Fusion (PLIF)
- (3) Transforaminal Lumbar Interbody Fusion (TLIF)
- (4) Oblique Lateral Interbody Fusion (OLIF) / eXtreme Lateral Interbody Fusion (XLIF)
- (5) Posterolateral Fusion (PLF)
- (6) Others (textbox)

When using InductOs in lumbar interbody spine fusion, how much rhBMP-2 do you usually implant in one intervertebral space?

- 1- Less than 4 mg
- 2- Between 4 mg and 8 mg
- 3- Between 8 mg and 12 mg
- 4- More than 12 mg

What best describes your use of the following tools, provided to physicians, when considering the use of InductOs or administering InductOs to a patient?

Tool	Never use	Sometimes use	Frequently use	Always use
Summary of				
Product				
characteristics /				
Package insert				
Educational				
materials				
Other				
information				
provided by the				
Market				
Authorisation				
Holder				
Information				
from peers				
Scientific				
publications				

Would you consider that the available information on the use and administration of InductOs is easy to access?

Y/N

(Note: for the questions below the following legend applies:

- Green text indicates a correct answer
- Orange text indicates a (sub)question which is considered for assessing awareness)

Which of the following are common adverse reactions you associate with InductOs when administering InductOs during lumbar interbody fusion?

1		37 / NT
1-	Urinary retention	Y / N
2-	Fluid collection, like localised edema or (pseudo)cyst	Y/N
3-	Malignancies	Y/N
4-	Neuralgia	Y / N
5-	Osteolysis / increased bone resorption	Y/N
6-	Pseudarthorsis	Y / N
7-	Radiculopathic complaints (radiculitis, radicular pain, radiating	Y / N
	pain, sciatica)	
8-	Heterotopic / ectopic ossification / additional bone growth	Y/N
9-	Back pain	Y / N
10-	Infections	Y / N
11-	Retrograde ejaculation	Y / N
12-	Others, please specify	Y / N

As the terms ectopic and heterotopic ossification are used interchangeably in some publications, we will use heterotopic ossification to describe both concepts. Heterotopic

ossification is one of the known adverse reactions to InductOs. Can you please indicate for each of the following statements whether it is true or false?

1	Heterotopic ossification can occur during lumbar arthrodesis	True / False
2	Heterotopic ossification occurs with and without the use of InductOs	True / False
3	Heterotopic ossification forms quickly	True / False
4	Heterotopic ossification can lead to nerve compression	True / False
5	Radicular pain is never the result of heterotopic ossification	True / False
6	Heterotopic ossification can occur asymptomatic	True / False
7	Heterotopic ossification occurs more often in patients undergoing a surgery with an anterior approach than in surgery with a posterior approach.	True / False

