#### 9.3 Variables

Information is collected on three main categories, details are described below. The first category is used to describe the population and includes variables around demographics, type of practice, and level of experience in using InductOs. The second category of variables is aimed at measuring the awareness on the risk of heterotopic ossification, the educational materials and knowledge about safe use of InductOs presented in the educational materials. The third set of variables covers the different sources where information on the key messages in the educational materials could have been obtained. A transcription of the intended survey is included in Annex 3.

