## First category:

- Physician specialty
- Practice type/hospital
- Years of practicing physician
- Years InductOs is used

- Last time InductOs was implanted
- Number of patients implanted with InductOs in the past 2 years
- Surgical approaches used
- Amount of rhBMP2 used in lumbar interbody spine fusion in one intervertebral space

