## 9.5 Study size

The minimum sample size needed to obtain a proportion with confidence interval with the lower limit above the 80 % minimum awareness was calculated. For this calculation an alfa of 0.05 with a two-sided interval and a distance from proportion to limit of 0.1 was used with the expected proportion of 90 %. This leads to a minimum sample size of 35.

To ensure inclusion of data from the different participating countries, this study aims at collecting responses from physicians covering roughly 10 % of purchasing pharmacies that have received InductOs in the past 2 years in each target country. However, if a greater number of respondents complete the questionnaires for a given target group, these responses will be integrated into the analyses.

The following number of completed surveys are planned per country:

France: 15Germany: 15

- United Kingdom: 15

- Ireland: 10

This brings the total to 55 completed surveys which is above the calculated minimum sample size. Taking into account response rate of roughly 60 % and screening failures an estimated 120 surgeons will be screened for eligibility.

Recruitment rate will be monitored by the researchers; and if it becomes apparent that the there is a risk of the study not meeting the recruitment target then other countries with InductOs sales will be included in the study to widen the pool of potential participants. In the selection of additional countries for recruitment, priority will be given to countries where the existing translated materials are used.

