## 9.7 Data analysis

The study population will include all physicians who are screened, are eligible for this study, and completed the questionnaire. All statistical summaries in this study will be descriptive. Frequencies and percentages, with 95 % confidence intervals (CIs) where appropriate, will be presented. Country specific data will be presented. Additional exploratory analyses and sensitivity analyses may be conducted to identify difference between groups of responders.

The primary analysis is aimed at evaluating the proportion of physicians that is aware of the risk of heterotopic ossification and measures described in the educational materials to minimize that risk. A respondent is considered to be aware if they answer 75 % of the questions with regards to heterotopic ossification and the applicable minimization measures correctly. In the questionnaire there are 12 (sub)questions raised on the occurrence of heterotopic ossification and the related risk minimization measures. Hence a surgeon needs to answer 9 of these correct to be considered aware. In Annex 3 the (sub)questions included in the scoring of awareness are marked. The aRMM will be considered effective if 80 % of the respondents are aware of the described risk of heterotopic ossification and the appropriate measures to minimize them. With the targeted 55 respondents, this means 44 or more need to be aware.

The secondary analysis is aimed at identifying the source of physician knowledge. Based on the received data it will be determined to what extent the educational materials are used and are considered an important source of information for the respondents.

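### The rhBMP-2 amount item gives exactly 8 mg two answer boxes, so the reported split between the two middle bands is not fully determined by practice

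*Protocol*

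**What the plan says.** Protocol Annex 3, under the InductOs questions, asks "how much rhBMP-2 do you usually implant in one intervertebral space" and offers four bands. The lowest is below 4 mg, the highest is above 12 mg, and the two between them are "Between 4 mg and 8 mg" and "Between 8 mg and 12 mg". No instruction says how to treat the limits.

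Section 9.3 lists the item among the first-category variables as "Amount of rhBMP2 used in lumbar interbody spine fusion in one intervertebral space", and states that "The first category is used to describe the population". Section 9.7 plans frequencies and percentages, with confidence intervals where appropriate, and adds that "Country specific data will be presented". Section 9.5 sets the planned completed surveys at 15 each for France, Germany and the United Kingdom and 10 for Ireland, 55 in total.

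**The concern.** A banded answer list should give every possible value exactly one box. Here 8 mg is named as a limit of two adjacent bands. Two surgeons with the same usual amount can therefore tick different boxes, and the reported distribution would show a difference in practice that does not exist. The same could happen between countries.

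This is a matter for the questionnaire and cannot be left to the analysis plan. Once only a band has been recorded, no later rule can recover the amount. The consistency and completeness checks in section 9.8 would not detect the problem, because either answer is plausible and complete.

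What is at stake is the description of usual dose, overall and by country, and any exploratory grouping of respondents by dose. The awareness result is not at stake.

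**Working it through.** **Which box takes each limit.** The outer labels exclude 4 mg and 12 mg. The word used for the middle bands can be read in two ways:

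| Amount | Boxes if the limits are included | Boxes if the limits are excluded |
|---|---|---|
| 4 mg | 1 | 0 |
| 8 mg | 2 | 0 |
| 12 mg | 1 | 0 |

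The inclusive reading is the sensible one, because otherwise 4 and 12 mg would have no box at all. Under it, 8 mg is the only amount with two boxes. On neither reading does 8 mg have exactly one.

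**Extraction error is not the cause.** The dose labels are written in words, so a lost inequality sign cannot explain the overlap. The patient-number item in the same questionnaire uses half-open bands (for example 10 to < 15 and 15 to < 20), which avoid the problem. The dose item does not carry that convention over. Items that allow several answers say so, and this one does not, so a single tick is the natural reading.

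**Plan figures involved.** The planned total reproduces: 3 × 15 + 10 = 55. So do the awareness rule (0.75 × 12 = 9) and the criterion (0.80 × 55 = 44). The dose item has no stated figure of its own. It stands before the scoring legend and does not ask about heterotopic ossification, so it contributes to neither 9 nor 44.

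**Size of the ambiguity.** Let k be the number of respondents at exactly 8 mg. They may all tick the lower band, all tick the upper band, or divide in any way. The share in either middle band can then lie anywhere in an interval of width k/n. This is the maximum effect. For one such surgeon:

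- Overall: 1/55 = 1.8 points
- France, Germany or the United Kingdom: 1/15 = 6.7 points
- Ireland: 1/10 = 10.0 points

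The protocol does not give the share at 8 mg. Assumed values, for all 55 respondents:

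| Assumed share at 8 mg | k of 55 | Maximum shift, points |
|---|---|---|
| 0 % | 0 | 0.0 |
| 5 % | 3 | 5.5 |
| 10 % | 6 | 10.9 |
| 20 % | 11 | 20.0 |
| 30 % | 16 | 29.1 |
| 50 % | 28 | 50.9 |

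**Comparison with sampling error.** The widest 95 % half-width at n = 55 is 1.96 × √(0.25/55) = 13.2 points. Seven surgeons at 8 mg give 7/55 = 12.7 points, which is below it. Eight give 8/55 = 14.5 points, which is above it.

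**Check of the relabelled bands.** With < 4, 4 to < 8, 8 to 12 and > 12 mg, each of 4, 8 and 12 mg has exactly one box, and the ambiguity is zero for any k.

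**The case against.** The strongest reply is that nothing the study must decide depends on this item. No research question concerns dose, no analysis by dose band is prespecified, and section 9.7 says only that exploratory comparisons may be done. The lowest band, the highest band and the two middle bands combined remain usable. All of this is right, and it is why the point is minor.

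A second reply is that the effect may be nil. No dose distribution is given, k/n is a worst case, and a question about usual practice in bands 4 mg wide is coarse by design. This also stands as a limit on size. It does not show that the labels are adequate, because coarse bands can still be made not to overlap.

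A third reply is that the pilot in section 9.1 tests the form for clarity. That helps, but two pilot surgeons need not include one who uses 8 mg, and such a surgeon may tick a box without remarking on it.

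A fair caution applies to the neighbouring items. As extracted, the years-in-practice item and the item asking "How many years have you been using InductOs" both show a 6 to 10 band beside a band of 10 or more, so year 10 would have two boxes. The top patient-number band appears as more than 20, which would leave exactly 20 without a box. These readings depend on symbols that may have changed in conversion from the PDF and should be checked against the original form. The dose finding does not rely on them.

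**Conclusion.** The concern holds and is minor. Exactly 8 mg has no unique box, no rule in the protocol assigns it, and the loss cannot be repaired after data collection. The share in either middle band is uncertain by at most the share of respondents at 8 mg. That share is unknown and may be near zero, so the percentages for 5 % to 50 % at 8 mg are assumptions and not estimates. The per-surgeon shifts rest on the planned counts in section 9.5 and would change if recruitment differed. The awareness proportion, the effectiveness criterion and the minimum sample size of 35 are unaffected.

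**What to change.** Relabel the four answers as < 4 mg, 4 to < 8 mg, 8 to 12 mg and > 12 mg. Alternatively, collect the usual amount in mg as a number and band it at analysis, which also keeps the detail. This implies no recommendation about dose.

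In the same edit, check the original symbols in the two years items and the patient-number item. If they are as extracted, change the top years band to > 10 in both items and the top patient band to ≥ 20.

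The cost is an edit to answer labels before translation and programming, with no effect on sample size or timeline.

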# 7. Rationale and background

The active ingredient of InductOs is dibotermin alfa or recombinant human Bone Morphogenetic Protein 2. Its osteoinductive properties result in the induction of new bone tissue at the site of implantation.

InductOs is approved for:

- single-level lumbar interbody spine fusion as a substitute for autogenous bone graft in adults with degenerative disc disease who have had at least 6 months of non-operative treatment for this condition.
- treatment of acute tibia fractures in adults, as an adjunct to standard care using open fracture reduction and intramedullary unreamed nail fixation.

Instructions for proper preparation and administration of dibotermin alfa/ACS are provided in the Summary of Product Characteristics (SmPC) and instructions for reconstitution are provided in the labelling of the pack. The aforementioned instructions consist of routine measures to minimise important identified (heterotopic ossification, osteolysis/resorption bone increased, fluid collection) and potential risks (medication errors and incorrect use, malignancies, antibody formation) by providing information on the measures to take during administration of dibotermin alfa/ACS or situations to avoid.

Additional risk minimisation measures (aRMM) to increase awareness about the identified risk of heterotopic ossification (especially in posterior surgical approaches for lumbar interbody fusion) and the potential risk of medication errors and misuse are available in the form of educational materials. These educational materials also aim at providing guidance on how to manage these risks. The aRMM present the information from the Summary of

Product Characteristics (SmPC) supported with visual aids, e.g. a demonstration of the correct preparation technique. The aRMM and related educational materials contain no information which is not contained in the SmPC.

InductOs educational materials consist of a preparation guide, two videos (one for each indication), and the SmPC. The educational materials can be accessed through a dedicated website, or upon request to the MAH.

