# 8. Research question and objectives

The goal of this study is to assess the awareness of InductOs-using spine surgeons concerning heterotopic ossification in relation to the InductOs Risk Management Plan. A supplementary goal of this study is to gauge the clinician's awareness about the development of heterotopic ossification and the risk minimisation measures; specifically identifying from which source was any knowledge obtained.

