## Secondary question:

• Was the knowledge on the risk of heterotopic ossification and minimization measures obtained from the SmPC, educational materials, professional training and literature, or a combination of these?

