#### *Third category*

- Used sources for guidance on InductOs administration
- Use of educational materials

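### The questionnaire records how often information tools are used, not where knowledge of heterotopic ossification came from, so the secondary question cannot be answered as worded

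*Protocol*

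**What the plan says.** The secondary question appears in the PASS information table, the abstract and section 8 of the protocol: "Was the knowledge on the risk of heterotopic ossification and minimization measures obtained from the SmPC, educational materials, professional training and literature". The question also allows several sources together. Section 8 gives the same aim as a supplementary goal: "specifically identifying from which source was any knowledge obtained". Section 9.7 says the secondary analysis is to identify the source of physicians' knowledge. It will also establish how far the educational materials are used and whether respondents see them as an important source.

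Section 9.3 describes the relevant variables more loosely: "The third set of variables covers the different sources where information on the key messages in the educational materials could have been obtained". The list beneath it has two entries, use of the educational materials and "Used sources for guidance on InductOs administration".

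Annex 3 has one item on sources: "What best describes your use of the following tools, provided to physicians, when considering the use of InductOs or administering InductOs to a patient". It is a grid with four answers (never, sometimes, frequently, always) and five rows: SmPC or package insert, educational materials, other information from the marketing authorisation holder, peers, and scientific publications. The only other item on information is a yes/no question: "Would you consider that the available information on the use and administration of InductOs is easy to access". The remaining items cover demographics, practice with the product, and knowledge.

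On what the materials are, section 7 states: "InductOs educational materials consist of a preparation guide, two videos (one for each indication), and the SmPC". It adds that they contain nothing beyond the SmPC.

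**The concern.** The research question is about the origin of a specific piece of knowledge. The questionnaire item is about current habits of consulting tools. These can differ for the same person. As a hypothetical case, a surgeon who learned about HO once from a video and never reopened it would answer never for the educational materials. Another who opens the package insert at every operation, but learned about HO in training, would answer always for the SmPC and have nowhere to record the training.

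At stake is a stated objective of the study. If the survey is fielded as printed, the report will either leave the secondary question unanswered or present frequency of use as if it were source of knowledge. This is not a detail that a statistical analysis plan could supply, because the information is never collected.

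**Working it through.** The protocol gives no figure for this point. Its one computed size, 35, concerns the primary proportion. It reproduces as 1.96² × 0.90 × 0.10 / 0.10² = 34.57, rounded up to 35, and has no bearing here. The check is therefore a comparison of content.

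**Step 1: sources named in the secondary question (section 8) against the rows of the grid (Annex 3).**

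| Source named in the question | Row in the grid |
|---|---|
| SmPC | Yes (SmPC / package insert) |
| Educational materials | Yes |
| Literature | Yes (scientific publications) |
| Professional training | None |

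Three of the four named sources are covered. Two of the five rows, peers and other information from the marketing authorisation holder, match no named source. Either might catch some training, but neither is labelled that way, and the grid has no free-text row.

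**Step 2: what each planned statement needs against what is collected.**

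| Planned statement | Needs | Collected in Annex 3 |
|---|---|---|
| Source of knowledge on HO and its minimisation (sections 8, 9.7) | An item linking source to HO knowledge | No item |
| Whether the materials are an important source (section 9.7) | An importance rating or ranking | No item |
| Extent of use of the materials (sections 9.3, 9.7) | Frequency of use | Yes, the grid |
| Sources used for guidance on administration (section 9.3) | Frequency of use by source | Yes, the grid, apart from training |

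The narrower variables in section 9.3 are largely met. The secondary question and the importance statement are not.

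**Step 3: could the answer be derived indirectly?** Section 9.7 allows exploratory comparisons between groups of responders, so awareness could be tabulated by tool use. With the planned 55 completed surveys, the unaware group would be about 55 × (1 − 0.90) = 5.5 at the protocol's expected 90 % awareness, or 55 × (1 − 0.80) = 11 at 80 %. Spread over four answer categories for each tool, these are very small counts. The table would show association only, and it still would not contain training.

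**Step 4: the SmPC and educational-materials rows.** By section 7 the SmPC is one component of the educational materials. The printed item does not say what the educational-materials row covers. A surgeon who reads only the SmPC could reasonably answer on one row or on both, so a use figure for the materials may partly be a use figure for the SmPC.

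**The case against.** The strongest reply is that the secondary analysis is not empty. The grid measures both third-category variables of section 9.3 and answers the part of section 9.7 on how far the materials are used. Section 9.3 speaks only of sources from which information could have been obtained. On this view the secondary question is simply worded more broadly than the variables. That stands as a limit on the point: a reader might infer that nothing useful is collected, and the documents do not support that. It does not remove the mismatch, because sections 8 and 9.7 still state the broader aim.

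A reader might also infer that the SmPC and the educational materials must be mutually exclusive rows. They need not be: the question lists them separately and allows a combination. What remains is an undefined label that makes the two rows hard to interpret.

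The opening of section 9.3 can be read as promising a measure of awareness of the materials themselves: "The second category of variables is aimed at measuring the awareness on the risk of heterotopic ossification, the educational materials". The second-category list below it contains no such variable, and the materials appear under use in the third category. The sentence is too ambiguous to count as a broken promise. Even so, a never answer does merge surgeons who do not know of the materials with those who know them but do not consult them.

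A never-to-always scale also gives some relative ordering of tools. That is a weak proxy for importance, not a measure of it.

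Finally, section 9.10 relies on a short survey to limit non-response, so adding items has a price.

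**Conclusion.** The point holds in this form. One of the four named sources has no row, no item links any source to HO knowledge, and no item asks importance. The secondary question as worded and the importance statement in section 9.7 therefore cannot be answered from Annex 3. Use of the SmPC, the educational materials and publications can be reported. The overlap between the SmPC and the educational materials is a lesser matter of interpretation.

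Two stronger conclusions are tempting and should not be drawn. First, the primary result is not affected: the effectiveness criterion in section 9.7 rests only on 80 % of respondents being aware (44 of 55), and the source item does not enter it. Second, a better source item would not let the study attribute knowledge to the additional risk minimisation measures. This is a one-time survey without a comparator. Any source item records self-report, about materials available since summer 2017, and is open to the social-desirability bias that section 9.10 acknowledges.

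The verdict assumes that the questionnaire in Annex 3 is the one to be fielded.

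**What to change.** Before the pilot:

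- Add a professional-training row to the grid.
- State in the item what the educational-materials row covers: the preparation guide and videos, with the SmPC reported on its own row. Because section 7 counts the SmPC among the materials, note in section 9.3 that this split is for reporting.
- Add a not-aware-of option to the grid.
- After the knowledge section, add one item asking from which source or sources the respondent learned about HO with InductOs and how to minimise it. Respondents tick all that apply and mark the most important. Options: SmPC, preparation guide or videos, professional training, literature, peers, other. Placing it last avoids prompting the adverse-reaction item, which asks whether HO is one of the reactions.
- Name this item in sections 9.3 and 9.7 as the secondary variable, reported as self-reported source and not as causal attribution.

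The cost is a slightly longer survey and some added translation. The documents give no completion time, so the extra burden cannot be quantified from them. Making the change before the pilot matters: under section 9.2, substantial changes afterwards would exclude the two pilot surgeons.

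The minimum alternative needs no change to the questionnaire. Restate the secondary question, the supplementary goal in section 8 and the secondary analysis in section 9.7 as frequency of tool use, and drop the source-of-knowledge and importance claims. The price is that the study no longer addresses where the knowledge came from.
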